7.4 Health-related Quality of Life Analyses Set

All randomized subjects will be included in Health-related Quality of Life Analyses Set.

7.5 Pharmacokinetic/Pharmacodynamic Analyses Set

All subjects who participated in the intensive PK/PDn substudy or the sparse PK sampling will be included in the Pharmacokinetic/Pharmacodynamic Analyses Set. These subjects will be evaluated for pharmacokinetics and pharmacodynamics unless significant protocol deviations affect the data analysis or if key dosing, dosing interruption, or sampling information is missing.

7.6 Interim Analyses Set

The interim analyses set will include all randomized subjects. The independent safety reviews, which are scheduled to occur approximately every 6 months, will include all randomized subjects for efficacy analyses and all treated subjects at the time of the database snapshot for a given review.

Statistical Analysis Plan: 20140355

Date: 09 Jun 2017 Page 22

7.7 Subgroup Analyses

Exploratory subgroup analyses for the primary endpoint and key secondary endpoints (ORR and OS) will be performed for each level of the three randomization stratification factors: International Staging System (ISS) Stage at study entry (Stage 1 vs. Stage 2 or 3), Refractory to bortezomib treatment (Yes vs. No) and Age (< 65 vs. \geq 65 years, <75 vs. \geq 75). Additional subgroup analyses will be based on the following factors:

- Sex (male vs. female)
- Race (White vs. Asian vs. Other)
- Ethnicity (Hispanic or Latino vs. Not Hispanic or Latino)
- Geographic region (Europe vs. North America vs. Asian Pacific)
- Baseline ECOG (0 vs. 1)
- Baseline creatinine clearance (30 < 50 ml/min vs. 50 < 80 ml/min vs. ≥ 80 ml/min)
- FISH risk group (high risk vs. standard risk vs. unknown)
- β2 microglobulin level (< 3.5 mg/L vs. ≥ 3.5 mg/L)
- ISS stage at baseline (Stage I vs. Stage II and III)
- ISS stage at diagnosis (Stage I vs. Stage II and III vs. Unknown)
- Corrected calcium at baseline (≤11.5 mg/dL vs. >11.5 mg/dL)
- Lines of prior treatment (2 vs. 3)
- Prior transplant (Yes vs. No)
- Prior lenalidomide (Yes vs. No)
- Refractory to lenalidomide (Yes vs. No)

These subgroups, except for stratification variables, will be re-examined and appropriately re-categorized before unblinding. Subgroup analysis containing a subgroup of less than 5% of the whole population will not be conducted.

8. Interim Analysis and Early Stopping Guidelines

One interim analysis will be conducted for PFS when approximately 263 (75% of total 350) PFS events are observed. The objective of the interim analysis is to monitor for differences between treatment arms for evidence of a substantial benefit in the carfilzomib once-weekly with dexamethasone arm.

To ensure proper control of type I error rate, the interim and final analysis of PFS will be analyzed under a group sequential design framework with the stopping boundaries constructed using the Lan-DeMets spending function with an O'Brien-Fleming approach. The stopping boundaries in an example scenario are calculated using East 6.4 and presented in Table 3. Actual boundaries will be calculated on the basis of observed PFS events up to the data cut-off date for the interim analysis.

Statistical Analysis Plan: 20140355

Date: 09 Jun 2017 Page 23

An external independent Data Monitoring Committee (DMC) will review the interim PFS analysis results and recommend whether the study should stop early for efficacy. If the DMC recommends to stop the study for efficacy, the sponsor will consider stopping the trial and conclude that the carfilzomib once-weekly with dexamethasone arm prolongs PFS compared to the carfilzomib twice-weekly with dexamethasone arm. In addition, the DMC will assess safety approximately every 6 months. An Independent Biostatistics Group (IBG) will perform the analyses and provide the interim reports to the DMC. The IBG and DMC will have access to subjects' individual treatment assignments. To minimize the potential introduction of bias to the conduct of the study, members of the DMC and IBG will not have any direct contact with study center personnel or subjects. The DMC will communicate major safety concerns and recommendations regarding study modification or termination based on the safety and efficacy parameters to Amgen in accordance with the DMC charter.

Records of all meetings will be maintained by the DMC for the duration of the study.

Records of all meetings will be stored in the Amgen official document management system at the conclusion of the study. Further details are provided in the DMC charter.

9. Data Screening and Acceptance

9.1 General Principles

The objective of the data screening is to assess the quantity, quality, and statistical characteristics of the data relative to the requirements of the planned analyses. The database will be subject to edit checks outlined in the data management plan by Amgen Clinical Data Management (CDM) department.

Statistical Analysis Plan: 20140355

Date: 09 Jun 2017 Page 24

9.2 Data Handling and Electronic Transfer of Data

The Amgen Global Study Operations-Data Management (GSO-DM) department will provide all data to be used in the planned analyses. This study will use the RAVE database. Laboratory data will be collected by COVANCE Central Laboratory Services and transferred to Amgen GSO-DM weekly in cumulative files. Quality of life data will be collected by ERT and transferred to Amgen GSO-DM monthly in cumulative files.

9.3 Handling of Missing and Incomplete Data

The descriptive statistics will identify the extent of missing data. Rules for handling missing data related to endpoints are described in the endpoint definitions (Section 6) or in the description of analyses (Section 10). The handling of incomplete and partial dates for adverse events and concomitant medications are described in Appendix B. Handling of missing or incomplete data for Exposure-Response (E-R) analysis will be described in the documents to support population PK/PDn dataset generation and E-R analysis.

9.4 Detection of Bias

Methods to detect bias are described in the analyses of particular endpoints (Section 10).

9.5 Outliers

Any suspected outliers will be investigated by the study team and will be included in the database unless determined to be an error or there is supporting evidence or explanation to justify the exclusion. Any outliers excluded from the analysis will be discussed in the Clinical Study Report (CSR), including the reasons for exclusion and the impact of their exclusion on the study. PK concentration data will be evaluated for outliers by visual inspection, and decisions to re-assay individual samples will be made in accordance with standard PKDM practice.

9.6 Distributional Characteristics

The statistical assumptions for analysis methods will be assessed. If the assumptions for the distributional characteristics are not met, these will be described and further analyses may be carried out using data transformations or alternative analysis methods. The use of transformations or alternative analysis methods will be justified in the final study report.

9.7 Validation of Statistical Analyses

Programs will be developed and maintained, and output will be verified in accordance with current risk-based quality control procedures.

Date: 09 Jun 2017 Page 25

Tables, figures and listings will be produced with validated standard macro programs where standard macros can produce the specified outputs.

The production environment for statistical analyses consists of Amgen-supported versions of statistical analysis software, for example the SAS System version 9.3 or later. For the PK/PDn analysis, refer to section 10.7 for software used.

10. Statistical Methods of Analysis

10.1 General Principles

[figure not shown]
Continuous variables will be summarized by the non-missing sample size (n), mean, standard deviation, median, minimum, and maximum. Categorical variables will be summarized by the n and percentage in each category. Time to event endpoints will be summarized with Kaplan-Meier (KM) curves, KM proportions at select time points, KM quartiles (when estimable), the number of subjects with events, the number of subjects censored, and censoring reasons. Duration of follow up for time to event endpoints will be estimated using the reverse Kaplan Meier method (Schemper and Smith 1996). Point estimates for efficacy endpoints will be accompanied by 2-sided 95% confidence intervals including estimates of KM quartiles (Klein and Moeschberger, 1997), KM proportions (Kalbfleisch and Prentice, 1980), and binomial proportions (Clopper CJ and Pearson, 1934). To examine non-proportionality between the treatment groups for time to event endpoints, the log cumulative hazard curves will be plotted. The scaled Schoenfeld residuals by time plot will be examined for evidence of a non-zero correlation, which indicates non-proportionality. Interaction between treatment and the log event time will be also tested at 10% level in a Cox model stratified by randomization stratification variables to test for non-proportionality

The hypotheses for the primary efficacy endpoint, PFS, and secondary efficacy endpoints (ORR and OS) will be tested using a fixed sequence hierarchical testing procedure to control the family-wise Type I Error rate below 1 sided 0.025 level. The family of hypotheses is ordered as follows: 1) PFS, 2) ORR, and 3) OS. Starting with the hypothesis of PFS, if any hypothesis in the sequence is rejected, then the subsequent hypothesis will be tested; if any hypothesis is accepted, then the subsequent hypotheses will not be tested. Furthermore, potential multiplicity from testing at two possible times of PFS IA and final analysis for ORR and OS will be adjusted using the Lan-DeMets spending function with an O'Brien-Fleming approach and a Pocock approach respectively (Hung et al 2007).

Statistical Analysis Plan: 20140355

Date: 09 Jun 2017 Page 26

10.2 Subject Accountability

The number and percent of subjects who were screened, randomized, received study treatment, entered long-term follow-up before disease progression and long-term follow-up for survival will be summarized by treatment group. The number and percent of subjects who discontinued study treatment, long-term follow-up before disease progression, and study will be tabulated, along with the reason for discontinuation. The number and percent of subjects randomized will be tabulated by the stratification factors. The number and percent of subjects randomized will be tabulated by study site. Key study dates for the first subject randomized, last subject randomized, and data cut-off date for analysis will be presented.

10.3 Important Protocol Deviations

Important Protocol Deviations (IPDs) categories are defined by the study team before the first subject's visit and updated during the IPD reviews throughout the study prior to database lock. These definitions of IPD categories, sub-category codes, and descriptions will be used during the course of the study. Eligibility deviations are defined in the protocol.

10.4 Demographic and Baseline Characteristics

Demographic (ie, age, age group [<65, 65-74, 75-84, ≥85], sex, race, and ethnicity) and baseline disease characteristics will be summarized by treatment group and overall using descriptive statistics for the Primary Analysis Set. The baseline characteristics to be summarized include:

Statistical Analysis Plan: 20140355

Date: 09 Jun 2017 Page 27

- Geographic region (Europe, North America, Asian Pacific)
- Reproductive status
- Baseline ECOG
- Baseline laboratories including: hemoglobin, ANC, platelet count, and creatinine clearance
- Baseline LVEF (%)
- Time from initial multiple myeloma diagnosis to randomization (months)
- Measurable disease category
- M-protein heavy and light chain subtype
- FISH risk group
- Serum free light chain Kappa/Lambda ratio
- Presence of any plasmacytoma
- · Presence of any bone lesion
- · Corrected calcium at baseline
- β2 microglobulin level
- ISS stage at diagnosis
- ISS stage at baseline
- Lines of prior treatment
- Prior transplant
- Prior bortezomib
- Prior lenalidomide
- · Prior thalidomide
- · Refractory to bortezomib
- Refractory to lenalidomide

10.5 Efficacy Analyses

10.5.1 Analyses of Primary Efficacy Endpoint

1-sided stratified log-rank test, stratified by the randomization factors, will be used to compare PFS between treatment groups as primary inference. In addition, a hazard ratio with a 95% confidence interval will be estimated from a stratified Cox regression model. The KM summaries described in Section 10.1 will be performed by treatment group. The primary analysis will be performed on the Primary Analysis Set based on computational assessments. Sensitivity analyses will be performed using investigator assessments, Independent Review Committee (IRC) assessments, different censoring rules regarding use of new anti-myeloma therapy and different analysis population. The details are documented in table 5. The discordance between the results regarding progression status and timing from the internal computational assessment, investigator and IRC will be summarized. Subgroup analyses will be performed to explore the consistency of the treatment effect for subgroups described in Section 7.7. Piecewise Cox models for 3-month time intervals may be explored given evidence of non-proportional hazards

Statistical Analysis Plan: 20140355

Date: 09 Jun 2017 Page 28

(Collett, 2003). This model will allow estimation of an overall weighted hazard ratio (weights equal to fraction of total events in each interval (Lu & Pajak, 2000)) as well as within interval treatment hazard ratio. Additional analysis may be performed to explore potential sources for non-proportionality by considering baseline prognostic factors and other potential confounding factors.

10.5.2 Analyses of Secondary Efficacy Endpoints

The ORR will be analyzed at the time of the PFS analysis (interim or final), only if the PFS analysis crosses the stopping boundary. The ORR will be calculated by treatment group and the associated 95% CI will be estimated using the Clopper Pearson method. The inferential comparison of ORR between treatment groups will be performed using Cochran-Mantel-Haenszel test stratified by the randomization stratification factors. 1-sided p-value from the test will be compared against the alpha value specified in Table 4 to determine the significance. Odds ratio (and its 95% CI) will be estimated using Mantel-Haenszel method. The primary analysis of ORR will be based on computational assessments for the Primary Analysis Set. Sensitivity analyses will be performed based on investigator assessments, Independent Review Committee (IRC) assessments, unstratified method, and for Per Protocol Set. The discordance between the results from the internal computational assessment, investigator and IRC will be summarized. Subgroup analyses will be performed to explore the consistency of the treatment effect for subgroups described in Section 7.7.

The analysis of OS will be conducted at the time of the PFS analysis (interim or final), only if both PFS and ORR analyses are positive. The same method as for analysis of PFS will be used for analysis of OS. The primary analysis of OS will be performed on the Primary Analysis Set. Sensitivity analyses will be performed based on unstratified analyses, and for Per Protocol Set. Subgroup analyses will be performed to explore the consistency of the treatment effect for subgroups described in Section 7.7. Piecewise Cox models for 6-month time intervals may be explored given evidence of non-proportional hazards.

Statistical Analysis Plan: 20140355

Date: 09 Jun 2017 Page 29

Table 5. Endpoint Summary Table

Endpoint	Primary Summary and Analysis Method	Sensitivity Analysis				
Primary Endpoint						
Progression-Free Survival	Based on internal computational assessments: KM summaries 1-sided p-value from stratified log-rank test Hazard ratio and 95% CI from stratified Cox	 Investigator assessments: same as primary summary and analysis method based on investigator assessments. IRC assessments: Same as primary summary and analysis method based on IRC assessments. 				
	regression	Unstratified analyses: 1-sided p- value from unstratified log-rank test, hazard ratio and 95% CI from unstratified Cox regression.				
		Initiation of new anti-myeloma therapy treated as PFS Event: The data censoring rules are the same as those for the primary analysis of PFS except that the use of new anti-myeloma therapy will be treated as an event rather than a mechanism for censoring. The same analysis method as for primary analysis will be used.				
		Initiation of new anti-myeloma therapy treated as neither a PFS event nor a censoring event: The data censoring rules are the same as those for the primary analysis of PFS except that the initiation of new anti-cancer therapy will be excluded as a mechanism for censoring. The same analysis method as for primary analysis will be used.				
		Per-Protocol subset: same as primary summary and analysis method for Per-Protocol subset.				
		Lost to follow-up or withdrawal of consent treated as event: The data censoring rules are the same as those for the primary analysis of PFS except that subjects who were lost to follow-up or withdrew consent without PD/ death are treated				

Statistical Analysis Plan: 20140355

Date: 09 Jun 2017 Page 30

		as having an event at the next scheduled assessment time in both treatment arms. The same analysis method as for primary analysis will be used.
Secondary Endpoints		
Overall Response Rate	Based on internal computational assessments: Point estimate of ORR and 95% CI by treatment group using the Clopper Pearson method 1-sided p-value from Cochran-Mantel - Haenszel test stratified byrandomization stratification factors Odds ratio associated with 95% CI using Mantel-Haenszel method	 Investigator assessments: Same as primary summary and analysis method based on investigator assessments. IRC assessments: Same as primary summary and analysis method based on IRC assessments. Unstratified analyses: 1-sided pvalue is from Fisher exact test and odds ratio (95%CI) estimate is not adjusted for randomization stratification factors. Per-Protocol subset: Same as primary summary and analysis method for Per-Protocol subset.
Overall Survival	 KM summaries 1-sided p-value from stratified log-rank test Hazard ratio and 95% CI from stratified Cox regression 	 Unstratified analyses: 1-sided p-value from unstratified log-rank test, hazard ratio and 95% CI from unstratified Cox regression. Per-Protocol subset: same as primary summary and analysis method for Per-Protocol subset.

10.5.3 Exploratory Efficacy Analysis

The KM summaries described in Section 10.1 will be performed by treatment group for duration of response and clinical benefit.

Time to response will be summarized by the non-missing sample size (n), mean, standard deviation, median, minimum, and maximum for responders by treatment group.

QLQ-C30, QLQ-MY20 and EQ-5D-5L questionnaires will be administered prior to study treatment on Day 1 of Cycle 1, then every second cycle (Cycle 1, 3, 5, etc) during treatment and every 12 weeks (every 84 days ± 4 days) until progression, or withdrawal of consent during LTFU. Patient convenience and satisfaction questionnaire will be collected at Cycle 2 and EOT only. All QLQ-C30 and QLQ-MY20 subscale scores will

Statistical Analysis Plan: 20140355

Date: 09 Jun 2017 Page 31

be summarized descriptively by visit and by treatment group using the number of subjects with non-missing data (n), mean, standard deviation, median, minimum and maximum. Change from baseline will be summarized using the same statistics. EQ-5D-5L data will be summarized by presenting the frequency and proportion of each level for each dimension by visit and by treatment group. EQ VAS data arm will be summarized using the same method for QLQ-C30 and QLQ-MY20 subscale scores. Patient convenience and satisfaction questionnaire has only two questions about whether the patients feel the carfilzomib dosing schedule convenient and how statisfied/dissatisfied they are with the dosing schedule. The frequency and proportion of each category will be summarized for the two questions by treatment group at cycle 2 and EOT. The comparison analyses of health-related quality of life between treatment groups will be implemented in addition to the descriptive analyses described above. For instance, Global Health Status/QoL scale, an important subscale of QLQ-C30, will be compared between treatment groups across visits using a restricted maximum likelihood-based mixed model for repeated measures (MMRM) under the assumption of missing at random (MAR) (Mallinckrodt et al, 2008).

10.6 Safety Analyses

10.6.1 Adverse Events

The Medical Dictionary for Regulatory Activities (MedDRA) version 19.1 or later will be used to code all adverse events (AE) to a system organ class and a preferred term. AEs of interest (EOI) categories will be based on search strategies defined by the EOI steering committee. All adverse event tables will be summarized by treatment group.

The subject incidence of AEs will be summarized for all treatment-emergent AEs, ≥ grade 3 TEAEs, serious AEs, AEs leading to modification (i.e., dose reduction or dose interruption) of investigational product, AEs leading to withdrawal of investigational product, and fatal AEs.

Subject incidence of all treatment-emergent AEs, ≥grade 3 TEAEs, serious AEs, AEs leading to modification (i.e., dose reduction or dose interruption) of investigational product, AEs leading to withdrawal of investigational product, and fatal AEs will be tabulated by system organ class and preferred term in descending order of frequency; similar summaries will be repeated for EOIs. Time to onset and duration of select EOIs may also be summarized.

Summaries of treatment-emergent AEs and serious AEs will be presented by preferred term in descending order.

Statistical Analysis Plan: 20140355

Date: 09 Jun 2017 Page 32

A summary of treatment-emergent AEs will be tabulated by system organ class, preferred term, and causal relationship to study drug.

A summary of treatment-emergent AEs will be tabulated by system organ class, preferred term, and worst grade based on NCI-CTCAE Version 4.03.

Subgroup analyses (if there is a medical rationale) will be presented by system organ class and preferred term or EOI in descending order of frequency.

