13.3.3.1 Adverse Events

Treatment-emergent adverse events are defined as AEs that start on or after the first day study treatment is administered and within 30 days of the last administration of study treatment. The reported AE term will be coded using MedDRA and will be graded for severity using NCI-CTCAE Version 4.03. The causal relationship between the occurrence of an AE and each treatment will be assessed by the investigator as related or not related.

Treatment-emergent adverse events will be summarized based on the number and percentage of subjects experiencing events by treatment group and by MedDRA system organ class (SOC) and preferred term. In the event that a patient experiences repeated episodes of the same AE, the subject will be counted once within each SOC and similarly counted once within each preferred term and the event with the highest severity grade and/or strongest causal relationship to each treatment will be used for purposes of incidence tabulations.

Tabular summaries of the following will be provided:

- All TEAEs by SOC
- All TEAEs in decreasing order of frequency
- TEAEs by causal relationship to study drug
- TEAEs by maximum severity grade
- All SAEs by SOC
- All SAEs in decreasing order of frequency
- TEAEs resulting in modification (i.e., dose reduction or dose interruption) of study treatment
- TEAEs resulting in discontinuation of study treatment
- Deaths within 30 days of the last administration of study treatment
- All AEs, including TEAEs, will be included in individual patient listings.

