2.2 Secondary Objectives

The secondary objectives of the study are to compare the following between treatment groups:

- Overall response rate (ORR)
- Overall survival (OS)
- Safety and tolerability
- Pharmacokinetics (PK) of carfilzomib using sparse sampling

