3.1 Study Design

This is an open label, multicenter, randomized Phase 3 study comparing once weekly carfilzomib dosing in combination with dexamethasone to twice weekly carfilzomib dosing in combination with dexamethasone in subjects with relapsed and refractory multiple myeloma, 2 or 3 prior therapies, and previously treated with a proteasome inhibitor and an IMiD. The primary endpoint is PFS. The study design is illustrated in Figure 1.

Eligible subjects will be randomized in a 1:1 ratio to receive a regimen consisting of either once-weekly or twice weekly carfilzomib in combination with dexamethasone.

The randomization will be stratified by:

- International Staging System (ISS) Stage at study entry (Stage 1 versus Stage 2 or 3) per International Myeloma Working Group (Greipp 2005).
- Refractory to bortezomib treatment (Yes versus No)
- Age (< 65 versus ≥ 65 years)

Study treatment will be administered in 28 day cycles. Subjects will receive the study treatment determined by randomization until disease progression, unacceptable toxicity, withdrawal of consent, or death (whichever occurs first). No crossover between the 2 treatment groups will be allowed.

Following termination of study treatment, all subjects will be followed for disease status (if progressive disease [PD] has not been reached), subsequent antimyeloma treatment, and survival.

[figure not shown]
All subjects will be followed for safety for at least 30 additional days after the last study treatment administration. All treatment-related adverse events (AEs) and serious adverse events (SAEs) will be followed until resolution or stabilization.

Statistical Analysis Plan: 20140355

Date: 09 Jun 2017 Page 9

Figure 1 Study 20140355 Schema

ECOG = Eastern Cooperative Oncology Group; IMiD = immunomodulatory agents; IV = intravenous(Iy); ORR = overall response rate; OS = overall survival; PD = disease progression; PFS = progression-free survival; PI = proteasome inhibitor; PO = orally.

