Time to response will be calculated only for subjects who achieve a best overall response of PR or better, i.e., sCR, CR, VGPR, or PR. It will be calculated in months from randomization date to the earliest date a response of PR or better is first achieved and subsequently confirmed:

Time to Response=(response start date-randomization date +1)/30.4

Treatment-emergent Adverse Event

Statistical Analysis Plan: 20140355

Date: 09 Jun 2017 Page 20

AEs starting on or after first dose of investigational product as determined by the flag indicating if the adverse event started prior to the first dose on the Events CRF and up to and including 30 days after the end of study treatment.

7. Analysis Subsets

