10.6.5 Exposure to Investigational Product

Descriptive statistics will be produced to describe the exposure to investigational product by treatment group for subjects in the Safety Analysis Set. The number of cycles of protocol-specified therapy administered will be summarized with an additional breakdown of the number of cycles started. In addition, the duration of therapy, the cumulative dose, and the average dose per administration and relative dose intenstiy will be summarized for each drug. The number and percent of subjects with dose modifications (eg, dose reductions, dose interruptions) and reason for modification will be summarized for both treatment groups.

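### All committed adverse-event comparisons are crude percentages of subjects, although time at risk depends on time on treatment and can differ between the arms

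*SAP*

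**What the plan says.** Safety and tolerability is a secondary objective, and SAP Section 2.2 introduces that list with "The secondary objectives of the study are to compare the following between treatment groups". The analysis is in SAP Section 10.6.1: "The subject incidence of AEs will be summarized for all treatment-emergent AEs", and likewise for grade 3 or higher, serious and fatal events and events leading to modification or withdrawal of treatment. The same summaries are repeated for EOIs. Protocol Section 13.3.3.1 agrees: "Treatment-emergent adverse events will be summarized based on the number and percentage of subjects experiencing events by treatment group".

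SAP Section 3.1 sets no fixed treatment length: "Subjects will receive the study treatment determined by randomization until disease progression, unacceptable toxicity, withdrawal of consent, or death". The treatment-emergent window in SAP Section 6 runs "up to and including 30 days after the end of study treatment", so time at risk follows time on treatment.

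Three items come near the issue:
- SAP Section 10.6.1 has an optional line: "Time to onset and duration of select EOIs may also be summarized".
- SAP Section 10.6.5 tabulates "the duration of therapy, the cumulative dose, and the average dose per administration" by arm, but not as a denominator for adverse events.
- SAP Section 10.7.1 relates safety endpoints to Cmax and AUC in subjects with PK samples. That is drug exposure, not time at risk.

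Neither document plans an exposure-adjusted rate, a cumulative incidence of adverse events, or incidence in a common time window.

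**The concern.** A crude percentage counts everyone who has the event before their window closes. If one arm stays on treatment longer, its subjects have more time in which to have an event, and its percentage rises even when the monthly risk is the same. The trial's hypothesis is that once-weekly dosing prolongs PFS. Progression ends treatment, so success on the primary endpoint would tend to lengthen the once-weekly arm's time at risk. If instead one arm stops sooner for toxicity, its shorter window could conceal part of that toxicity.

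Protocol Section 2.4 pairs superior efficacy with an acceptable safety profile, so the adverse-event tables will carry weight in the benefit-risk reading. As planned, they give no measure of event occurrence that takes time at risk into account.

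**Working it through.** **Inputs.** From the current documents: 350 PFS events, one-sided alpha 0.025, one interim at 263 events, 83% power (Protocol Section 13.5), and a 30-day tail after treatment. The current effect assumption is redacted. Superseded text in Protocol Appendix O gives median PFS of 6 months (twice-weekly) and 8.2 months (once-weekly) with a hazard ratio of 0.73. These are used only as assumptions.

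**The plan's own figure.** Without an interim, the power argument is |ln 0.73| × √350 / 2 − 1.96 = 2.944 − 1.960 = 0.984, which gives 83.7%. With a Lan-DeMets O'Brien-Fleming boundary at 263 and 350 events (nominal one-sided p 0.0097 and 0.0221), power is 83.1%. The stated 83% is reproduced, so the superseded effect is consistent with the current design.

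**Model.** Time on treatment is exponential with rate μ = ln 2 / median: 0.1155 per month twice-weekly and 0.0845 once-weekly. Mean durations are 8.66 and 11.83 months, a ratio of 1.37. The hazard h of a first event is the same in both arms. The tail is taken as 1 month.

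**1. Persistent hazard.** Crude incidence = 1 − e^(−h) × μ/(μ + h). At h = 0.05 this is 1 − 0.9512 × 0.1155/0.1655 = 33.6% twice-weekly and 1 − 0.9512 × 0.0845/0.1345 = 40.2% once-weekly.

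**2. Other stopping added.** Replace μ by μ + 0.03 in both arms. The 0.03 is an assumption, with some support in Protocol Section 2.5.1. There, once-weekly 70 mg/m² had median PFS of 10.6 months and median treatment durations of 8.3 and 7.2 months. As exponentials, ln 2/8.3 − ln 2/10.6 = 0.018 and ln 2/7.2 − ln 2/10.6 = 0.031 per month.

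| h per month | Case 1: twice-weekly vs once-weekly | Gap | Case 2: twice-weekly vs once-weekly | Gap |
|---|---|---|---|---|
| 0.02 | 16.4% vs 20.7% | 4.3 | 13.8% vs 16.6% | 2.7 |
| 0.05 | 33.6% vs 40.2% | 6.6 | 29.2% vs 33.8% | 4.6 |
| 0.10 | 51.5% vs 58.6% | 7.1 | 46.4% vs 51.7% | 5.3 |

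Gaps are in percentage points, from unrounded values. The true rate ratio is 1.00 in every row.

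**3. Hazard confined to months 0 to 2.** Ignoring the tail, incidence = h/(h + μ) × (1 − e^(−2(h + μ))). With h set to give 10%, 30% and 50% in the twice-weekly arm, the once-weekly arm shows 10.3%, 30.8% and 51.3%. The gap is 0.3 to 1.3 points.

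**4. What a rate does in case 3.** Mean time to first event or end of treatment = (1 − e^(−2(h + μ)))/(h + μ) + e^(−2(h + μ))/μ. At 30% incidence (h = 0.203) this is 6.06 months twice-weekly and 8.18 once-weekly. The rate ratio is (0.3085/8.18) / (0.3000/6.06) = 0.76, although the hazards are equal. Across 10% to 50% incidence it is 0.76 to 0.77.

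**The case against.** The strongest reply has four parts.

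- **Direction.** A reader might infer that longer PFS will make once-weekly dosing look more toxic. The documents do not support that. It needs a hazard that persists and treatment time that tracks PFS, but progression is one of nine listed reasons for stopping (Protocol Section 11.1), and early-onset events show almost no gap. This part stands: the claim is *can*, and the direction is not fixed.
- **What a reader will see.** One might also infer that nothing in the plan would reveal an exposure artefact. That goes too far. Cycles, treatment duration, dose intensity, reasons for stopping, and adverse events leading to modification or withdrawal are all committed by arm. Laboratory values, vital signs and the QLQ-MY20 side-effects scale are summarised by visit. These show whether exposure differed. They do not show how much of an adverse-event difference it explains.
- **Estimand.** Crude incidence validly answers how many subjects assigned a regimen have the event while on it, longer stay included. That stands, and is why the crude tables should remain. The monthly risk is a separate question that the objective also raises.
- **Remedy.** Rates alone would bring a bias of their own, as step 4 shows. This stands and shapes the fix.

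The adverse-event tables carry no test, so an inference that type I error is inflated would be wrong.

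**Conclusion.** The point holds as a gap in the descriptive safety analysis, worth closing because it is cheap. Every committed adverse-event comparison is crude subject incidence, and no committed analysis relates event occurrence to time at risk. The range is about 4 to 7 points with a persistent hazard, 3 to 5 with added non-progression stopping, and about 1 or less for events in the first 2 months. It rests on exponential durations, superseded medians used as treatment durations, and equal hazards by construction. Unequal stopping for toxicity could shrink or reverse it. Primary inference and trial conduct are unaffected.

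**What to change.** In SAP Section 10.6.1, before unblinding:

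1. Keep all crude percentages.
2. Add first-event exposure-adjusted incidence rates per 100 patient-years by arm for all treatment-emergent, grade 3 or higher, serious, fatal and EOI categories. Time at risk runs from first dose to first event or the end of the treatment-emergent window.
3. For EOIs and grade 3 or higher events, add time-to-first-event cumulative incidence by arm, or incidence in a common early window. If cumulative incidence is used, state whether end of treatment plus 30 days is a competing event or censoring. The first converges to the crude percentage, and the second assumes that stopping is unrelated to event risk.
4. Change *may* to *will* for time to onset of EOIs.
5. State that the rates assume a roughly constant hazard and are to be read beside item 3, since they can favour the longer-treated arm for early-onset events (ratio about 0.76 in step 4).

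The cost is a few more tables from dates already collected. Rates added after unblinding would be post hoc and could look chosen to suit one arm.
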